### **6.2.1.2 Permitted concomitant therapy for the management of SCD-related priapism**

Concomitant prophylactic treatment for SCD-related priapism is permitted provided the subject has been prescribed the same medication consistently for at least 14 weeks prior to screening as per inclusion criterion 7. Dosing should not be altered or terminated other than for safety during the duration of the study. In subjects not on prophylactic medications, treatment should not be initiated during the study. If a physician deems it necessary to terminate or alter treatment during the study, the monitor must be notified immediately to determine whether the subject may continue the study.

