2.5.3 Handling of intercurrent events

The imputation of missing data caused by intercurrent events will be handled by defining the estimand framework.

The primary estimand is described by the following four attributes:

1. The target population comprises Sickle Cell Disease Patients with Priapism.
2. The primary variable is percent reduction from baseline period in priapic events (priapism defined as unwanted, or painful erection lasting at least 60 min self-reported) by 26 weeks.
3. Treatment of interest: investigational drug will be a crizanlizumab solution provided every 4 weeks with an additional loading dose 2 weeks after the first dosing.
4. The intercurrent events are the events occurring after enrollment that may impact the treatment effect. The intercurrent events of interest are listed below:
 - a. Treatment discontinuation
 - b. Initiation or discontinuation of HU/HC or l-Glutamine (or other therapies to treat SCD and or to prevent/reduce VOCs such as voxelotor and erythropoietin) or of prophylactic treatment for priapism
 - c. Intake of analgesic (including opioids) or ad hoc transfusions administered temporarily
5. The summary measure is the median percentage change from baseline period in priapic events (priapism defined as unwanted, or painful erection lasting at least 60 min self-reported) by 26 weeks.

Handling of the intercurrent events:

The approach of accounting for intercurrent events is as follows:

- **For the intercurrent events 4a:** Only data before study treatment discontinuation will be included. The data between treatment discontinuation and week 26 will be imputed using Poisson distribution (primary method to handle missing data as described in [Section 2.5.4](#)).
- **For the intercurrent events 4b:** Only data before initiation or discontinuation of HU/HC or L-Glutamine (or other therapies to treat SCD and or to prevent/reduce VOCs such as Voxelotor and erythropoietin) or of prophylactic treatment for priapism will be included. The data between initiation or discontinuation of therapies to treat SCD or of prophylactic treatment for priapism and week 26 will be imputed using Poisson distribution (primary method to handle missing data as described in [Section 2.5.4](#)).
- **For the intercurrent events 4c:** Data after intake of analgesic (including opioids) or ad hoc transfusions administered temporarily will be included (treatment policy strategy).

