2.6.1 Secondary endpoint(s)

The secondary objectives in this study are to assess efficacy, safety and tolerability of crizanlizumab 5.0 mg/kg in SCD subjects.

The following secondary efficacy endpoints will be analyzed on all FAS subjects who have completed 26 and 52 weeks on treatment to evaluate clinical efficacy of crizanlizumab 5 mg/kg:

- a. The rate of priapic events by 26 and 52 weeks of treatment.
- b. The percent reduction from baseline in acute priapic events (defined as an unwanted, painful erection that lasts more than 4 hours and need a visit to emergency room) by 26 and 52 weeks of treatment. Note that, this analysis will only be performed if an adequate number of subjects are present.
- c. The rate of uncomplicated VOC events (defined as an acute event of pain with no known cause for pain other than a vaso-occlusive event; and requiring treatment with a parenteral or oral opioids or other parenteral analgesic; but is NOT classified as an acute chest syndrome, hepatic sequestration, splenic sequestration or priapism and these events will not be adjudicated) by 26 and 52 weeks of treatment. Events include both healthcare and self-reported events.
- d. The rate of complicated VOCs (defined as acute chest syndrome, hepatic sequestration, splenic sequestration, and acute priapism) recorded by healthcare visit, by 26 and 52 weeks of treatment.

The efficacy endpoints will be assessed and summarized by 26 weeks and by 52 weeks .

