2.6.2 Statistical hypothesis, model, and method of analysis

Similar analyses on percent reduction in acute priapic events for subjects from full analysis set will be conducted, as done for primary endpoint.

Annualized rates will be calculated for the secondary endpoints.

The annualized rate of events is defined as the total number of events for a subject occurring from the date of initial infusion to the last contact date of the Treatment Phase of the study x 365.25 divided by the number of days during that same time period. This calculation accounts for early dropouts or lost to follow-up by extrapolating the priapism events rate of every subject to 1 year.

Annualized events rate = Total number of events x 365.25 / (end date – treatment start date +1), where end date is defined as the minimum of (last dose date until treatment discontinuation + 27 days, date of initiation or discontinuation of HU/HC or L-glutamine - or other therapies to treat SCD and or to prevent/reduce VOCs such as voxelotor and erythropoietin, cut-off date).

Descriptive summary statistics including n, mean, standard deviation (SD), lower quartile (Q1), median, upper quartile (Q3), minimum, and maximum will be presented for the annualized rate of events and number of priapic events at Baseline, by Week 26 and by Week 52 .

The change from baseline in rates of events at Week 26 (i.e. evaluation at Week 27, Day 1) and Week 52 (i.e. evaluation at Week 53, Day 1) will be summarized by n, mean, median, standard deviation (SD), lower quartile (Q1), median, upper quartile (Q3), and minimum and maximum.

Graphical representation of annualized rates, through box plots or bar graphs or swimmer plot, as appropriate, will also be performed.

The Annualized Rates of Events at Week 26 (i.e. evaluation at Week 27, Day 1) and Week 52 (i.e. evaluation at Week 53, Day 1) will be summarized by n, mean, standard deviation (SD), lower quartile (Q1), median, upper quartile (Q3), standard deviation and minimum and maximum.

Additionally, cumulative number of acute priapic events, uncomplicated and complicated VOC events will also be summarized over time (like 0-12 weeks, 0-26 weeks, 0-40 weeks and 0-52 weeks).

Subgroup analyses displaying annualized rate, for complicated and uncomplicated VOC events will be performed based on use of hydroxyurea versus no use of hydroxyurea by 26 weeks and 52 weeks.

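### The annualised-rate end date omits changes in priapism prophylaxis, so the secondary rate of priapic events can be biased in either direction

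*SAP*

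**What the plan says.** SAP 2.6.1 lists as secondary endpoint (a) "The rate of priapic events by 26 and 52 weeks of treatment". SAP 2.6.2 then states "Annualized rates will be calculated for the secondary endpoints" and defines the end of each subject's period as the minimum of three dates:

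- "last dose date until treatment discontinuation + 27 days";
- the "date of initiation or discontinuation of HU/HC or L-glutamine - or other therapies to treat SCD and or to prevent/reduce VOCs such as voxelotor" or erythropoietin;
- the cut-off date.

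The list closes with "other therapies to treat SCD and or to prevent/reduce VOCs such as voxelotor and erythropoietin, cut-off date" and does not mention priapism prophylaxis.

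Intercurrent event 4b in SAP 2.5.3 covers the same SCD and VOC therapies, but its list runs on: "voxelotor and erythropoietin) or of prophylactic treatment for priapism". SAP 1.2.1 and Protocol 2.1 and 12.4.2 also name prophylaxis in 4b. For the primary endpoint, data after such a change are dropped and imputed. For the secondary endpoints, SAP 2.6.3 (intercurrent events) is marked not applicable.

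The sentence just before the formula in SAP 2.6.2 gives a different period: events "occurring from the date of initial infusion to the last contact date of the Treatment Phase of the study", with no stop for any therapy change. SAP 2.5.6 (supportive analysis 1) and Protocol 12.4.4 use that period too.

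Protocol 6.2.1.2 says subjects not on prophylaxis should not start it, and that dosing should not be altered or ended other than for safety. It adds: "If a physician deems it necessary to terminate or alter treatment during the study, the monitor must be notified immediately", so that a decision can be made on whether the subject continues.

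**The concern.** Priapism prophylaxis is the one class in the 4b list aimed directly at the event being counted, and it is the class missing from the rate formula. As written, the period ends when a subject starts voxelotor, which the protocol's Amendment 1 rationale describes as having no reported benefit on priapism. It does not end when a subject starts or stops a drug given to prevent priapism.

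The primary endpoint and secondary endpoint (a) count the same events, so a reader will expect them to corroborate each other. There is no control arm to absorb the effect of a concomitant change. Any prophylaxis effect therefore enters the on-treatment rate, and the change from baseline in that rate, as if it came from crizanlizumab. Acute priapism, one component of the complicated-VOC rate (endpoint d), is exposed in the same way.

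**Working it through.** **Is the omission real?** The two SAP lists match item for item (hydroxyurea, L-glutamine, other SCD or VOC therapies with voxelotor and erythropoietin as examples) until the last item, which only 4b has. The SAP document history shows Amendment 1 adding both the estimand text and this end date, and describes the latter as being for the rate of priapic events. SAP Section 4 does not list the difference as an intended change. The last-contact-date period also has no prophylaxis stop, so post-change data are kept under either definition in 2.6.2.

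**Inputs.**
- From the documents: 34 evaluable subjects and a mean of 10.0 events per 26 weeks (SAP Section 3). The windows are T = 182 days (first dose to the day before Day 183) and T = 364 days (to the day before Day 365), from SAP 2.1.1 and Table 2-1.
- Assumptions: crizanlizumab has no effect; the underlying rate is constant; prophylaxis cuts the rate by r = 30% to 50%; the start day is s.

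The documents give no figure for this bias. The section supplying 34 and 10.0 does reproduce: a mean difference of 2.5 with SD 5.0 and n = 34 gives 80.8% power by one-sample t test, against the stated 80%.

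**One subject who starts prophylaxis.** Days 1 to s−1 run at the full rate and the remaining T−s+1 days at (1−r) times it. The annualising factor cancels, so

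false fall = r × (T − s + 1)/T.

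| Start day | Share of time after start, T = 182 | Fall, r = 30% / 50% | Share, T = 364 | Fall, r = 30% / 50% |
|---|---|---|---|---|
| 91 | 92/182 = 0.505 | 15.2% / 25.3% | 274/364 = 0.753 | 22.6% / 37.6% |
| 29 | 154/182 = 0.846 | 25.4% / 42.3% | 336/364 = 0.923 | 27.7% / 46.2% |

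If the period is cut at the start date, the false fall is 0 under the constant-rate assumption.

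**One subject who stops prophylaxis.** If the rate then rises by a proportion u at week 13, the 26-week rate rises by u × 13/26. For u = 25%, 50% and 100% that is 12.5%, 25% and 50%. Stopping a drug that halved the rate corresponds to u = 100%.

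**Cohort mean, k of 34 subjects starting.** Take r = 50% and start days uniform over 52 weeks.
- 52 weeks: on average half the period follows the start, so each starter contributes 0.5 × 50% = 25%. The mean falls by k/34 × 25%: 1.5%, 2.9% and 4.4% for k = 2, 4 and 6. Simulating 4,000 cohorts gave 1.6%, 3.0% and 4.4%.
- 26 weeks: half the starters begin after week 26 and contribute nothing; the rest average half the window. Each starter contributes 0.5 × 0.5 × 50% = 12.5%, giving 0.7%, 1.5% and 2.2%.
- With r = 30% the 52-week range is k/34 × 15%: 0.9% (k = 2) to 2.6% (k = 6).

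**Precision cost of cutting.** A Day 29 change leaves 28 days. Expected events are 10 × 28/182 = 1.54, with a Poisson coefficient of variation of 1/√1.54 = 81%, annualised by 365.25/28 = 13.0. Over 52 weeks the figures are 20 events and 1/√20 = 22%.

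**The case against.** **The protocol restrains the favourable direction.** A reader might infer that the plan credits crizanlizumab with a fall caused by starting prophylaxis. The documents do not support that as a one-way claim. Protocol 6.2.1.2 says prophylaxis should not be started, and its continuation clause speaks of terminating or altering treatment, not of initiating it. Inclusion criterion 7 admits subjects already on prophylaxis, so stops are possible, and a stop counts against the drug. Event 4b does anticipate initiation, so starts cannot be ruled out. This objection narrows the point to a bias of either sign.

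**The per-subject figures are not trial effects.** Falls of up to 46% apply to one affected subject under an assumed effect. Across the cohort the mean moves by a few per cent, and the median, also reported, is generally less sensitive to a few subjects. A subject taken off treatment after a change is already limited by the last-dose-plus-27-days rule. All of this stands.

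**The VOC wording might already cover prophylaxis.** SAP Section 3 calls priapism a complicated VOC, so a therapy to prevent VOCs could be read to include it. But 4b uses the same phrase and still names prophylaxis separately, so at best the programmer must guess.

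**Parity with 4b is not required.** The SAP defines no secondary estimand, and the primary imputes where the rate truncates and extrapolates. That is true, and the rules would still differ after the fix. But the omission cannot be read as a declared treatment-policy choice: the formula stops at SCD-therapy changes, and SAP 2.6.3 states no strategy.

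**Cutting has its own bias.** If prophylaxis is started during a flare, a cut there and annualisation would overstate the rate. This stands, and is a reason to show both versions.

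**Conclusion.** The point holds as a specific inconsistency in a descriptive secondary summary. The SAP 2.6.2 end date does not stop at a start or stop of priapism prophylaxis, so endpoint (a) retains affected time and events: biased down by a start, up by a stop. If 2 to 6 of 34 subjects start a prophylactic that halves events, the false fall in the mean rate is about 1.5% to 4.4% by 52 weeks and about 0.7% to 2.2% by 26 weeks. Those figures rest on an assumed effect, a constant underlying rate, start days uniform over the year, and a number of subjects that the documents do not give. The primary analysis follows 4b, and the success rule in SAP 2.5.2 does not use this rate, so neither is affected. The change is worth making because it is cheap and the endpoint counts the same events as the primary.

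**What to change.** 1. In SAP 2.6.2, add the date of initiation or discontinuation of priapism prophylaxis to the end-date minimum for the rate of priapic events, matching event 4b.
2. In the same edit, make the preceding sentence in 2.6.2 (period to last contact in the Treatment Phase), and the same wording in SAP 2.5.6, agree with that end date. Record the departure from Protocol 12.4.4 in SAP Section 4.
3. For complicated VOC (endpoint d), keep one exposure period for the composite. If wanted, report acute priapism as a separate component rate with the prophylaxis cut, so that exposure periods are not mixed within one rate.
4. Show the uncut rate of priapic events alongside, with the number of subjects who start or stop prophylaxis.

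Cost: a few words and one more date in the derivation. Event 4b already needs that date for the primary analysis, so no new data are required. The downside is shorter follow-up, and so a noisier annualised rate, for subjects who change early.

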2.6.3 Handling of intercurrent events

Not applicable

2.6.4 Handling of missing values not related to intercurrent event

Not applicable

2.6.5 Sensitivity analyses

Not applicable

2.6.6 Supplementary analyses

Not applicable

2.7 Safety analyses

All safety analyses will be based on the Safety Set unless otherwise specified. Safety summaries include only on-treatment assessments. Safety listings include all assessments with those more than 105 days after last study treatment, flagged.

2.7.1 Adverse events (AEs)

For reporting of AEs, the overall observation period will be divided into three mutually exclusive segments:

1. Pre-treatment period: from day of subject's informed consent to the day before first dose of study medication
2. On-treatment period: from day of first dose of study medication to 105 days after last dose of study medication (or until EOT date for subjects continuing crizanlizumab after their EOT via commercial supply)
3. Post-treatment period: starting at Day 106 after last dose of study medication (or after EOT date for subjects continuing crizanlizumab after their EOT via commercial supply or a post-trial access program)

Reporting of AEs will be based on MedDRA version 25.0 or higher and the Common Terminology Criteria for Adverse Events (CTCAE) version 5.0 or higher.

AE summaries will include all AEs occurring during on-treatment period. All AEs collected in the AE CRF page will be listed along with the information collected on those AEs e.g. AE relationship to study drug, AE outcome etc. AEs outside of on-treatment period will be flagged in the listings.

Summary tables for AEs will include only AEs that started or worsened during the on-treatment period, the treatment-emergent AEs. The incidence of TEAEs (new or worsening from baseline) will be summarized by system organ class and or preferred term, severity (based on CTCAE grades), type of AE, relation to study treatment.

AEs will be summarized by number and percentage of subjects having at least one AE, having at least one AE in each primary system organ class (SOC) and for each preferred term (PT) using MedDRA coding. A subject with multiple occurrences of an AE will be counted only once in the respective AE category. A subject with multiple CTCAE grades for the same preferred term will be summarized under the maximum CTCAE grade recorded for the event. AE with missing CTCAE grade will be included in the 'All grades' column of the summary tables.

In AE summaries, the primary system organ class will be presented alphabetically and the preferred terms will be sorted within primary SOC in descending frequency. The sort order for the preferred term will be based on their frequency in all subjects.

Serious adverse events will be tabulated. All deaths (on-treatment death and post-treatment death) will be summarized.

All AEs and SAEs (including those from the pre and post-treatment periods) will be listed and those collected during the pre-treatment and post-treatment period will be flagged. SAEs will be summarized and listed.

Separate summaries for AEs by SOC and PT, summarized by relationship, seriousness, leading to treatment discontinuation, leading to dose interruption, requiring additional therapy and leading to fatal outcome.

In addition, for the legal requirements of clinicaltrials.gov and EudraCT, two required tables (plus standard safety XML files) on on-treatment adverse events which are not SAEs with an incidence greater than 5% and on on-treatment serious adverse events and SAEs suspected to be related to crizanlizumab will be provided by SOC and PT.

If for the same patient, several consecutive AEs (irrespective of study treatment causality, seriousness and severity) occurred with the same SOC and PT:

- A single occurrence will be counted if there is ≤ 1 day gap between the end date of the preceding AE and the start date of the consecutive AE.
- More than one occurrence will be counted if there is > 1 day gap between the end date of the preceding AE and the start date of the consecutive AE.

For occurrence, the presence of at least one SAE/SAE suspected to be related to crizanlizumab /non-SAE has to be checked in a block e.g., among AEs in a ≤ 1 day gap block, if at least one SAE is occurring, then one occurrence is calculated for that SAE.

The number of deaths resulting from SAEs suspected to be related to study treatment and SAEs irrespective of study treatment relationship will be provided by SOC and PT.

2.7.1.1 Adverse events of special interest / grouping of AEs

Not applicable

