#### **4.5 Risks and benefits**

Please refer also to the latest version of the Investigator Brochure for the most recent information on the efficacy and safety of crizanlizumab.

Results from the randomized, placebo-controlled SUSTAIN study in SCD patients (aged 16 years and older, any genotype) established the efficacy of crizanlizumab 5 mg/kg compared to placebo by showing a statistically significant and clinically meaningful reduction of the annual rate of VOC leading to healthcare visit. In addition, a more than a two-fold increase in the number of patients who remained completely free of VOC leading to healthcare visit during the study, and a three-fold increase in the median time to first VOC leading to healthcare was observed.

[figure not shown]
Pooled safety data from the SUSTAIN and CSEG101A2202 studies in patients treated with crizanlizumab 5 mg/kg (n=111 patients, Mar Oct 2019 cutoff) showed that crizanlizumab is generally associated with a favorable safety profile. Adverse drug reactions (ADRs) were nausea (16.2%), back pain (15.3%), arthralgia (14.4%), pyrexia (14.4%), abdominal pain (9.0%), diarrhea (8.1%), pruritus (7.2%), vomiting (5.4%), myalgia (4.5%), musculoskeletal chest pain (4.5%), oropharyngeal pain (3.6%), infusion site reaction (2.7%), and infusion-related reaction (1.8%).

In addition, in the randomized SUSTAIN study the overall frequency of AEs, SAEs and AEs leading to treatment discontinuation was similar among patients treated with crizanlizumab 5 mg/kg and placebo. Use of crizanlizumab in combination with HU/HC did not result in any meaningful differences in the safety profile.

Based on class effects, pre-/clinical findings, the mechanism of action of crizanlizumab, identified and potential risks include the following:

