##### **Infusion-related reactions (IRRs)**

Administration of monoclonal antibodies (mAbs) can be associated with IRRs. A focused search for potentially “severe” IRRs (i.e. indicative of hypersensitivity/anaphylaxis or cytokine-release syndrome) identified 3 (2.7%) patients treated with crizanlizumab 5 mg/kg in the pooled data set. The event reported for all 3 patients was “infusion-related reaction”, none of which was severe (all Grade 1 or 2, all non-serious), none required hospitalization or treatment discontinuation, and all events resolved without sequelae or complications on the same day.

However, severe IRRs including cases requiring hospitalization have been described in ongoing clinical trials and the post-marketing setting. Refer to Investigator's Brochure for additional details regarding these IRRs.

Additionally, a broad search for IRRs using an extensive list of potential signs and symptoms related to infusion reactions, and occurring within 24 hours of the infusion, identified 37 patients (33.3%) in the safety pool with at least one event. Most of these events were reported in 1 or 2 patients only, except for nausea (9.0%), headache (9 %), arthralgia (6.3%), back pain (4.5%), and fatigue, hypertension, dizziness, and myalgia (2.7%). None of the events were Grade 3 or 4 in severity. In the SUSTAIN study, IRRs using this broader search were more frequent in the 5 mg/kg arm (34.8%) compared to the placebo arm (21.0%). However, except for nausea, none of the events were reported with an absolute difference of more than 5% in the crizanlizumab 5 mg/kg vs. the placebo arm and none were severe. Based on post marketing reports, IRRs may present as pain, refer to Investigator's Brochure for additional details.

In summary, current data suggest that administration of crizanlizumab can be commonly associated with infusion related reactions, some of which can be severe and/or require hospitalization. Patients should be monitored for potential signs and symptoms of IRRs, and subjects instructed to contact the investigator/site when experiencing such events. In case of severe IRRs (eg. hypersensitivity/anaphylactic reaction), study treatment should be discontinued.

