### **Effect on hemostasis**

Considering the mode of action of crizanlizumab and physiological role of P-selectin, a potential effect on the hemostatic system was evaluated by searching for AEs related to hemorrhage, abnormal laboratory parameters. In the safety pool, a search for hemorrhagic events identified 16 (14.4%) patients. Except for prolonged prothrombin time, decreased hemoglobin, and epistaxis reported in 3 (2.7%) patients each, these events were reported in 1 or 2 patients only. None were Grade 4 or led to study withdrawal, and none were considered treatment related as per investigator assessment. The only Grade 3 event was decreased hemoglobin (2 patients), consistent with hemolysis and the underlying disease.

In Study A2201, hemorrhagic events were reported in 11 (16.7%) patients in the 5 mg/kg and 8 (12.9%) patients in the placebo arm, mostly related to laboratory abnormalities. Of note, 1 event (intracranial hemorrhage) reported in the 2.5 mg/kg arm was considered serious (Grade 4, hospitalization) and led to study drug discontinuation. Cerebrovascular accidents, including hemorrhagic stroke, are known complication and leading cause of death in patients with SCD.

In summary, bleeding events were rare, with the majority of the observed AEs being abnormal laboratory parameters on single occasions. The available data do not suggest an adverse effect of crizanlizumab on hemostasis. Nevertheless, subjects should be monitored for signs/symptoms of bleeding; additionally, hematology and coagulation parameters will be regularly assessed during the study.

A separate search for potential AEs related to thrombosis did further not identify any patients with AEs related to thrombosis in the 5 mg/kg pooled data, suggesting that crizanlizumab does not have relevant a pro-aggregant or pro-thrombotic effect.

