c Certain adverse events reported in the AE/SAE eCRF as Infusion Related Reactions will require the IRR eCRF to be completed.

d Local sampling for platelet assessment will be performed throughout the trial for all subjects.

e The date, number, and duration of the priapic events in the 14-week period prior to consenting will be captured in a separate CRF.

f Subjects who will receive commercially approved crizanlizumab approximately 4 weeks after their last dose of study treatment, do not need to complete the 105-day follow-up.

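### The SAP switches off all adverse-event grouping, so no planned summary gives a per-subject total of infusion-related reactions or ties events to the infusion

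*SAP*

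**What the plan says.** SAP 2.7.1.1, headed "Adverse events of special interest / grouping of AEs", is marked not applicable. SAP 2.7.1 plans counts of subjects with any AE, "having at least one AE in each primary system organ class (SOC) and for each preferred term (PT) using MedDRA coding", with breakdowns by grade, seriousness, relationship and action taken. It also mentions "type of AE, relation to study treatment" without defining the first of these. Protocol 12.6 names no IRR analysis either.

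Protocol Table 8-1 carries a continuous IRR row, and its footnote c reads: "Certain adverse events reported in the AE/SAE eCRF as Infusion Related Reactions will require the IRR eCRF to be completed". The current SAP text does not mention that form.

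Protocol 4.5 lists IRRs first among the identified and potential risks. It concludes that they are common and that some are severe or lead to hospitalization. For the pooled 5 mg/kg data ("n=111 patients, Mar Oct 2019 cutoff") it gives three figures:
- 1.8% for the event in the list of adverse drug reactions;
- 3 patients (2.7%) in a focused search for potentially severe reactions, all three reported under the term infusion-related reaction;
- a broad search of signs and symptoms within 24 hours of infusion, which "identified 37 patients (33.3%) in the safety pool with at least one event".

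In the randomized study the same broad search gave 34.8% on 5 mg/kg and 21.0% on placebo.

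**The concern.** Safety and tolerability is a stated objective, and the protocol itself measures this risk by grouped searches rather than by one preferred-term row. The symptoms its broad search names most often, such as nausea, headache, joint pain and raised blood pressure, belong to different organ classes. An organ-class and preferred-term table cannot say how many subjects had any of them around an infusion, or separate an infusion-day headache from one three weeks later.

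The study has no control arm, so its IRR experience can be read only against outside data. The earlier 34.8% and 21.0% are usable for that only if the same definition is applied here. If the definition is left open until the data are seen, the reported figure depends on which one is picked.

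**Working it through.** **1. Reproduce the protocol's pooled figures (Protocol 4.5, n = 111; exact 95% intervals).**
- Adverse-drug-reaction list: 2/111 = 1.8% (0.2 to 6.4).
- Focused search: 3/111 = 2.7% (0.6 to 7.7).
- Broad 24-hour search: 37/111 = 33.3% (24.7 to 42.9).

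All three reproduce. The first two differ by one patient for what reads as the same event in the same pool. The cut-off is printed as two months ("n=111 patients, Mar Oct 2019 cutoff"), so two data cuts are one possible reason, but the documents do not say.

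**2. How specific is the broad search?** Arm sizes follow from the bleeding counts in Protocol 4.5: 11/0.167 ≈ 66 on 5 mg/kg and 8/0.129 ≈ 62 on placebo. Then 23/66 = 34.8% and 13/62 = 21.0%, matching the text.
- Difference: 34.8 − 21.0 ≈ 13.9 points from the unrounded fractions.
- Standard error: √(0.348 × 0.652/66 + 0.210 × 0.790/62) ≈ 0.078.
- 95% interval: 13.9 ± 1.96 × 7.8, that is −1.4 to 29.2 points. Fisher exact p = 0.12.

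Much of what the broad search catches also occurs on placebo.

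**3. What is lost without the 24-hour link?** Compare the protocol's frequencies for the same term in the drug-reaction list, which states no time limit, with those in the broad 24-hour search:

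| Term | Drug-reaction list | Within 24 hours |
|---|---|---|
| Nausea | 16.2% (18/111) | 9.0% (10/111) |
| Back pain | 15.3% (17/111) | 4.5% (5/111) |
| Arthralgia | 14.4% (16/111) | 6.3% (7/111) |

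A preferred-term table without a time limit gives figures of the first kind. The second cannot be derived from it.

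**4. What is lost without the per-subject total?** Read 2.7% as applying to each of the last four terms named in the broad search. The eight named terms then give 10 + 10 + 7 + 5 + 4 × 3 = 44 term-level counts, before the rarer terms are added, yet only 37 patients are involved. Adding rows does not recover the number of subjects.

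**5. Scale here, assuming 36 treated subjects and that the earlier rates carry over.**
- Single term: 36 × 0.018 = 0.6 to 36 × 0.027 = 1.0 subject. The chance of none is 0.982^36 ≈ 52% to 0.973^36 ≈ 37%.
- Broad definition: 36 × 0.333 = 12 subjects.
- Broad definition at the placebo rate: 36 × 0.210 ≈ 7.5 subjects, with no drug effect at all.

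The documents do not give this trial's own rate. One subject in 36 is 2.8%.

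**The case against.** The strongest reply is that little of clinical weight is hidden. SAP 2.7.1 already tabulates serious events, grades, relationship, and events leading to discontinuation, interruption or additional therapy. Protocol Table 6-2 makes discontinuation mandatory for Grade 3 and 4 IRRs, so an event recorded that way should surface in those tables. Component symptoms keep their own rows. AEs and dosing are listed, with study day shown, so timing can be traced by hand for about 36 subjects. The SAP introduction places table and listing shells in a separate document, so the IRR eCRF may be listed there. The SAP also does not contradict Protocol 12.6, which asks for no grouping.

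Most of this stands, and it limits the point. It does not remove it: no stated summary gives the subject total or the infusion link, reading listings is not a prespecified analysis, and the grouping section is closed explicitly rather than left to the shells.

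A further objection is that a grouped count cannot be built from the protocol alone, because Protocol 4.5 names only the more frequent terms of its search. That is correct, so the sponsor has to supply the list. Lastly, a non-specific count in a single-arm trial has no concurrent control. That is also correct, and it is why the broad set should never be shown alone.

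**Conclusion.** The point holds as a gap in the safety analysis that is cheap to close. As written, the SAP gives no per-subject, infusion-linked summary of a risk the protocol calls common and sometimes severe, and it states no use of a form collected for that purpose. The protocol's own figures range from 1.8% to 33.3% in the same 111 patients according to definition, so the definition needs to be set before analysis.

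Three stronger readings are tempting and are not supported.
- A reader might divide 33.3% by 2.7% or 1.8% and infer that the preferred-term row would understate harm 12- to 18-fold. The broad figure is not a true IRR rate: 21.0% arose on placebo, the excess was about 14 points with an interval that includes zero, and the protocol reports no Grade 3 or 4 event in the pooled broad search.
- A reader might take IRRs to be the drug's main risk, or expect this trial's table to show about 2 to 3%. The protocol lists them first but does not rank them, and the projection to 36 subjects assumes that the old rates carry over.
- A reader might want bleeding grouped as well, since "In the safety pool, a search for hemorrhagic events identified 16 (14.4%) patients". The same section finds no sign of an adverse effect on hemostasis, and SAP 2.7.3 already summarizes the hematology and coagulation data. That grouping is optional.

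The conclusion rests on the SAP text; the table shells were not available.

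**What to change.** Replace the entry in SAP 2.7.1.1 with one IRR summary on the Safety Set, showing two definitions side by side:
- **Narrow:** the preferred term infusion-related reaction, plus every event with an IRR eCRF.
- **Broad:** the sponsor's search-term list behind Protocol 4.5, cited or appended in the SAP, with onset within 24 hours of an infusion. Protocol 10.1.1 asks for AE start dates. If times are not collected, use a start date on the day of the infusion or the day after, and label this as a wider window than the earlier search.

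Exclude imputed start dates from the broad set: SAP Table 5-1 can set a partial date to the first treatment date, which would create false infusion-day events. Show each set by maximum grade and by infusion number. Add a listing of the IRR eCRF. State with the table that the broad set is non-specific (21.0% on placebo in the earlier trial) and has no concurrent control here.

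Reconcile 1.8% with 2.7% in Protocol 4.5.

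The cost is a paragraph of SAP text, an appended term list, one summary table and one listing, all from data already collected. No dosing or clinical rule changes. The SAP history shows four amendments before database lock, and this change could take the same route; made after lock, it should be labelled post hoc.
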